7.8 Trial Outcome Measures

7.8.1 Primary outcome measure

Time to first COPD exacerbation.

7.8.2 Secondary outcome measures

Data pertaining to secondary outcomes will be collected over the entire trial follow-up (i.e. inclusive of time on IMP and if needed off IMP):

- Number/rate of exacerbations (and differentiation by severity of exacerbations, i.e. requirement of hospitalisation)
- Length of exacerbation-free status
- Antibiotics and/or corticosteroids use for respiratory indication
- Symptoms/impact: CAT score and cough visual analogue score (VAS)
- Health status (quality of life measured by change in EQ-5D-5L)
- Mortality (all cause and specific)
- Healthcare utilisation (for health economic analysis)
- Adverse events of special interest (AESI) (including cardiovascular and hearingdefined as new prescription of hearing aids, liver function test (LFT) dysfunction), serious adverse events (SAEs)
- Sputum culture results, if clinically indicated and sample via routine clinical care to local lab. Record if positive result (i.e. name of organism cultured only, not cfu/ml). If multiple sent, most recent one to trial visit should be used.
- Adherence to trial medication.

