- All adverse events and adverse reactions will be recorded for the same period of time described above.
- Hospitalisations for treatment planned prior to randomisation and hospitalisation for elective treatment of a pre-existing condition will **not** be considered, recorded or reported as an SAE.
- Complications occurring during such hospitalisation will also not be considered, recorded or reported as an SAE unless there is a possibility that the complication arose because of the trial medication (i.e. a possible adverse reaction).
- Exacerbations of COPD, pneumonia or hospital admissions as a consequence of exacerbations of COPD or pneumonia will **not** be considered or reported as AEs or SAEs because they are primary and secondary outcomes for the trial. These will be recorded as part of the trial outcomes.

All other SAEs (including SARs) should be reported to the lead site trial office (see front cover of the protocol and SAE Form for SAE reporting contact information).

11.1.5 Suspected Unexpected Serious Adverse Reaction (SUSAR)

A serious adverse reaction, the nature and severity of which is not consistent with the information set out in the Reference Safety Information.

11.1.6 Reference Safety Information (RSI)

A list of medical events that defines which reactions are expected for the IMP within a given trial and thus determining which Serious Adverse Reactions (SARs) require expedited reporting.

The RSI is contained in a clearly identified section of the Summary of Product Characteristics (SmPC) or the Investigator's Brochure (IB).

For this trial, the Reference Safety Information is:

Section 4.8 of the SmPC of Azithromycin 250mg film coated Tablets (Accord-UK Ltd) approved by the MHRA for use in this trial.

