11.3 Expected Adverse Events/Serious Adverse Events (AE/SAE)

Exacerbations of COPD or hospital admissions as a consequence of exacerbations of COPD will **not** be considered as AEs or SAEs because they are primary and secondary outcomes for the trial. These will be recorded as part of the trial outcomes, and therefore not reported as AEs or SAEs.

Adverse events of special interest (AESI) that will be evaluated in the trial include those below. These may also require SAE reporting.

New major adverse cardiovascular events (MACE):
Myocardial infarction
Stroke
Cardiovascular death
Development of arrhythmias
Hearing (for example new prescription of hearing aids)
LFT dysfunction

These will be recorded separately to all other AEs, to enable ease of data analysis.

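### Section 11.1.4.1 exempts pneumonia from AE/SAE reporting as a trial outcome, but no outcome or AESI names pneumonia and the parallel exemption in 11.3 omits it

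*Protocol*

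**What the plan says.** Protocol section 11.1.4.1, which sets the operational rules for adverse events, lists "Exacerbations of COPD, pneumonia or hospital admissions as a consequence of exacerbations of COPD or pneumonia" as events that will not be "considered or reported as AEs or SAEs because they are primary and secondary outcomes for the trial". It then names the substitute route: "These will be recorded as part of the trial outcomes". All other SAEs go to the lead site trial office.

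Section 11.3 returns to the subject with a shorter list. It begins "Exacerbations of COPD or hospital admissions as a consequence of exacerbations of COPD will" and gives the same reason, "because they are primary and secondary outcomes for the trial". Pneumonia is not mentioned. The AESI list that follows covers major cardiovascular events, arrhythmias, hearing and liver function.

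The primary outcome in 7.8.1 is "Time to first COPD exacerbation". The secondary outcomes in 7.8.2 include "Number/rate of exacerbations (and differentiation by severity of exacerbations, i.e. requirement of hospitalisation" and "Antibiotics and/or corticosteroids use for respiratory indication", together with mortality and healthcare utilisation. Pneumonia does not appear among them.

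**The concern.** Exempting disease-related events from SAE forms is ordinary practice when the same events are collected as endpoints: the safety route is closed because the outcome route is open. Here the safety route is closed for pneumonia, but no outcome is specified that would identify it.

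The trial withdraws an antibiotic, under blinding, in people with COPD at high risk of exacerbation, and adverse events are one of its secondary objectives. A comparison of pneumonia between continued, seasonal and no azithromycin is one that readers may reasonably ask for. As the protocol stands, the data to answer it would have to be pieced together from items not designed to label pneumonia. Sections 11.1.4.1 and 11.3 also give sites different lists, so whatever pneumonia data do arrive may depend on local reading.

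**Working it through.** No arithmetic applies; the check is a comparison of sections.

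**Step 1. Is pneumonia an outcome, as 11.1.4.1 says?** Each place where it could be named was read in turn:

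- Objectives (7.7): exacerbations, health status, hospitalisation and healthcare use, mortality, adverse events, subgroups, cost-effectiveness, adherence. Pneumonia not named.
- Outcomes (7.8.1, 7.8.2): not named.
- Follow-up content and schedule of assessments (10.5, 10.6): exacerbations and healthcare usage are collected; pneumonia not named.
- AESI list (11.3): not named.
- Response criteria (13.1): not named.

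Outside the 11.1.4.1 exemption, the word occurs only in the title of a cited reference.

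**Step 2. Do the two exemptions agree?**

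- 11.1.4.1 exempts COPD exacerbations, pneumonia, and admissions due to either.
- 11.3 exempts COPD exacerbations and admissions due to them.

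The rationale is the same and the scope differs. Hospitalisation is a seriousness criterion under 11.1.4. A site working from 11.3 would therefore report a pneumonia admission as an SAE, and a site working from 11.1.4.1 would not. About 135 sites are planned.

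**Step 3. Can pneumonia be read as an exacerbation, so that the primary outcome captures it?** The definition in 10.4.1 requires worsening COPD symptoms treated with additional antibiotics and/or oral corticosteroids. It neither includes nor excludes pneumonia. Section 8.8 distinguishes exacerbations from other infections, and 11.1.4.1 itself lists pneumonia alongside exacerbations as a separate item. A pneumonia meeting the definition could be logged as an exacerbation, but no rule says that it should be, and once logged it would not be distinguishable as pneumonia.

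**Step 4. Where else could it appear?**

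- Admissions: 10.4.16 records hospitalisations generally, and 10.5 and 10.7 provide for linked hospital records. No pneumonia category is specified, and 13.1.4 describes healthcare usage as that for COPD.
- Treatment: respiratory antibiotic or corticosteroid use is a secondary outcome, with no diagnosis attached.
- Death: 13.1.2 asks for cause of death where possible. The collated categories are all-cause, respiratory/COPD-related and cardiovascular.

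Each is an indirect route. None is specified to identify pneumonia.

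**The case against.** The strongest reply is that pneumonia is not lost. Hospitalisation and healthcare use form a secondary objective that 7.7.2 does not restrict to COPD, so a pneumonia admission falls within a stated objective. Respiratory antibiotic use and cause-specific mortality are secondary outcomes, and admissions and deaths are obtained by linkage. A pneumonia meeting 10.4.1 may be counted as an exacerbation. On this view the exemption is a deliberate design, 11.3 is merely silent on pneumonia rather than opposed to 11.1.4.1, and what remains is a matter of wording.

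Much of this stands. A reader might infer that a participant could die of pneumonia and leave no trace of it. The documents do not support that, because cause of death is to be recorded where possible. A reader might also infer that the data monitoring committee would never see pneumonia as a safety matter. That cannot be established: its remit is in a charter that is not shown, and the detailed data items are deferred to the trial procedures manual. Nor does the protocol describe pneumonia as a leading harm of stopping azithromycin; that would be a clinical judgement brought from outside.

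What the reply does not do is make the stated reason accurate. An admission outcome that may contain pneumonia is not an outcome that identifies it. Silence in 11.3 also has a consequence: an event not on an exemption list is reportable by default, so the two lists lead to different actions.

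**Conclusion.** The point holds in this form. The rationale in 11.1.4.1 is incorrect for pneumonia as a named event. Its exemption is wider than the one in 11.3, and following it leaves pneumonia unreported as an SAE and unidentified in any specified outcome. The defect is in the protocol's own reporting rules, so it is not something that an analysis plan would settle.

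Its size cannot be given. Under 11.1.4.1 the exemption applies to every pneumonia in every arm, but the documents state no pneumonia rate and do not say which section sites will follow. The point does not touch the non-inferiority margin, the sample size or the primary model. Its only link to the primary endpoint is the unsettled question of whether a pneumonia is logged as an exacerbation.

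The conclusion assumes that the unseen procedures manual and case report form do not already collect pneumonia by name. If they do, the data gap closes, but 11.1.4.1, 11.3 and 7.8.2 still need to be aligned.

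**What to change.** Reconcile 11.1.4.1 with 11.3 by one of two routes.

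- **Delete both mentions of pneumonia from the 11.1.4.1 exemption**, so that it matches 11.3 and ordinary AE/SAE reporting applies. This is the smallest edit. Under 11.1.4.1, however, reporting for participants who stop trial medication ends 28 days after they stop, so later pneumonias would not be covered.
- **Keep the exemption and make its reason true.** Add pneumonia, with hospitalisation and death, to the AESI list in 11.3 and to the secondary outcomes in 7.8.2, and repeat it in the 11.3 exemption. State that it is recorded separately from exacerbations and how the two are told apart. Section 7.8.2 already provides for secondary outcomes to be collected over the whole of follow-up, on and off trial medication, so this route gives the more complete comparison between arms.

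The cost is a wording amendment, a case report form item under the second route, and some extra SAE or AESI forms. Making the change early matters, because events not labelled as pneumonia when they occur may be hard to identify reliably afterwards.

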11.1.2 Adverse reaction to an investigational medicinal product (AR)

All untoward and unintended responses to an investigational medicinal product related to any dose administered. All adverse events judged by either the reporting investigator or The Sponsor as having a reasonable causal relationship to a medicinal product qualify as adverse reactions. The expression reasonable causal relationship means to convey in general that there is evidence or argument to suggest a causal relationship.

11.1.3 Unexpected adverse reaction

An adverse reaction, the nature, or severity of which is not consistent with the applicable reference safety information (RSI). When the outcome of the adverse reaction is not consistent with the applicable RSI, this adverse reaction should be considered as unexpected.

The term "severe" is often used to describe the intensity (severity) of a specific event. This is not the same as "serious," which is based on participant/event outcome or action criteria.

11.1.4 Serious adverse event or serious adverse reaction (SAE / SAR)

Any untoward medical occurrence that at any dose:

- results in death
- is life-threatening
- requires hospitalisation or prolongation of existing inpatient hospitalisation
- results in persistent or significant disability or incapacity
- is a congenital anomaly or birth defect
- is an important medical event Some medical events may jeopardise the participant or may require an intervention to prevent one of the above characteristics/ consequences. Such events (hereinafter referred to as 'important medical events') should also be considered as 'serious'.

Life-threatening in the definition of a serious adverse event or serious adverse reaction refers to an event in which the participant was at risk of death at the time of event; it does not refer to an event which hypothetically might have caused death if it were more severe.

11.1.4.1 Operational definitions for (S)AEs

In this trial

- SAEs will be reported from the time a participant consents to join the trial until the end of trial, if a participant remains on trial medication. Participants who withdraw from taking trial medication will have SAEs reported from the time the participant consents to join the trial until 28 days after ceasing trial medication. Participants who never start taking the trial medication will have SAEs reported for 28 days from the time they consent to join the trial.

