11.6 Reporting of Suspected Unexpected Serious Adverse Reactions (SUSARs)

All suspected adverse reactions related to an investigational medicinal product (the tested IMP and comparators) which occur in the concerned trial, and that are both unexpected and serious (SUSARs) are subject to expedited reporting. Please see section 11.1.6 for the Reference Safety Information to be used in this trial.

11.6.1 Who should report and whom to report to?

The Sponsor delegates the responsibility of notification of SUSARs to the CI. The CI must report all the relevant safety information previously described, to the

- Sponsor
- competent authorities in the concerned member states (e.g. MHRA)
- Ethics Committee in the concerned member states

The CI shall inform all investigators concerned of relevant information about SUSARs that could adversely affect the safety of participants.

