11.6.2 When to report?

11.6.2.1 Fatal or life-threatening SUSARs

All parties listed in 11.6.1 must be notified as soon as possible but no later than **7 calendar days** after the trial team and Sponsor has first knowledge of the minimum criteria for expedited reporting.

In each case relevant follow-up information should be sought and a report completed as soon as possible. It should be communicated to all parties within an additional **8 calendar days**.

11.6.2.2 Non-fatal and non-life-threatening SUSARs

All other SUSARs and safety issues must be reported to all parties listed in 11.6.1 as soon as possible but no later than **15 calendar days** after the trial team and Sponsor has first knowledge of the minimum criteria for expedited reporting. Further relevant follow-up information should be given as soon as possible.

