11.6.3 How to report?

11.6.3.1 Minimum criteria for initial expedited reporting of SUSARs

Information on the final description and evaluation of an adverse reaction report may not be available within the required time frames for reporting. For regulatory purposes, initial expedited reports should be submitted within the time limits as soon as the minimum following criteria are met:

a) A suspected investigational medicinal product

b) An identifiable participant (e.g. trial participant code number)

c) An adverse event assessed as serious and unexpected, and for which there is a reasonable suspected causal relationship

d) An identifiable reporting source

Also when available and applicable:

- A unique clinical trial identification (Clinical Trials.Gov number or in case of non-European Community trials The Sponsor's trial protocol code number)
- A unique case identification (i.e. The Sponsor's case identification number)

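### The protocol gives two non-equivalent SUSAR definitions: section 11.1.5 read literally is narrower than 11.1.3 taken with 11.6, and used alone it could leave a serious unexpected reaction unexpedited

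*Protocol*

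**What the plan says.** Five places in section 11 of the protocol bear on what counts as a SUSAR.

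- **11.1.3, unexpected adverse reaction.** The first limb uses *or*: "An adverse reaction, the nature, or severity of which is not consistent with the applicable reference safety information (RSI"). A second limb adds outcome as a sufficient ground: "When the outcome of the adverse reaction is not consistent with the applicable RSI, this adverse reaction should be considered as unexpected".
- **11.1.5, SUSAR.** The section headed as the definition uses *and*, and does not mention outcome: "A serious adverse reaction, the nature and severity of which is not consistent with the information set out in the Reference Safety Information".
- **11.1.6, RSI.** The RSI lists the reactions that are expected, "thus determining which Serious Adverse Reactions (SARs) require expedited reporting". The RSI for this trial is section 4.8 of a named azithromycin product summary.
- **11.6, expedited reporting.** Suspected reactions "that are both unexpected and serious (SUSARs) are subject to expedited reporting". The only definitional cross-reference here is to 11.1.6, not to 11.1.3 or 11.1.5.
- **11.6.3.1, minimum criteria.** Criterion (c) reads: "An adverse event assessed as serious and unexpected, and for which there is a reasonable suspected causal relationship".

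Section 11.5 also makes the CI responsible for having every SAE assessed for expectedness and relatedness. SUSAR status then sets the 7-day limit (11.6.2.1) or the 15-day limit (11.6.2.2). Under 8.5 it also makes the CI and the CCTU team responsible for unblinding.

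**The concern.** A SUSAR definition has to give one answer for one case. Here the section that carries the name sets a stricter test than the section defining unexpectedness and the sections that trigger reporting. Two assessors who each follow the protocol, one from 11.1.5 and the other from 11.1.3 and 11.6, can classify the same serious reaction differently.

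At stake are expedited notification of the competent authority and the ethics committee, and unblinding of the participant. The case most clearly affected is a reaction of a type already in the RSI that turns out worse than the RSI describes, or ends in a way it does not describe. An example is a fatal case of a reaction that the RSI lists without a fatal outcome.

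**Working it through.** There is no figure in the plan to reproduce, and nothing here touches power, alpha or event counts. The check is a comparison of the definitions over all logical cases.

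**Inputs.** Take a reaction that is serious and suspected to be caused by the IMP. Let N, S and O mean that its nature, severity or outcome is *not* consistent with the RSI.

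**Rules as written.**

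- Unexpected under 11.1.3: N or S or O.
- SUSAR under 11.6 and 11.6.3.1(c): serious, suspected and unexpected. For this reaction that again means N or S or O.
- SUSAR under 11.1.5 read literally: N and S. O plays no part.

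**Step 1: nature and severity only (outcome consistent).**

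| Nature | Severity | 11.1.3 with 11.6 | 11.1.5 literal |
|---|---|---|---|
| consistent | consistent | no | no |
| consistent | inconsistent | SUSAR | no |
| inconsistent | consistent | SUSAR | no |
| inconsistent | inconsistent | SUSAR | SUSAR |

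Three of four combinations are SUSARs by the first route and one of four by the second. The third row carries less weight. A reaction whose nature is not in the RSI has no listed severity to agree with, so an assessor might well count it as inconsistent on both. The second row has no such escape.

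**Step 2: listed nature, with outcome added.** Fix nature as consistent and vary severity and outcome, giving 2 × 2 = 4 combinations.

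- 11.1.3 with 11.6: all but the fully consistent one are SUSARs, so 4 − 1 = 3.
- 11.1.5 literal: N is false, so N and S is false throughout, giving 0.

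On its literal wording, then, 11.1.5 can never make a SUSAR of a reaction whose nature is listed, however severe it is and whatever its outcome.

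**Step 3: direction.** Whenever N and S is true, N or S or O is also true. Every SUSAR under 11.1.5 is therefore a SUSAR under 11.6, but not the reverse. The mismatch can only remove cases from expedited reporting and cannot add any.

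These are counts of logical combinations, not of expected cases. The protocol gives nothing from which to estimate how often each would occur.

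**The case against.** The strongest reply is that the operative rules are already right. Section 11.6 says what is expedited, 11.6.3.1(c) repeats the test without any joint condition on nature and severity, and 11.5 has every SAE assessed for expectedness, a notion defined only in 11.1.3. On that view a serious reaction of listed nature and unlisted severity is expedited, and 11.1.5 is a loose paraphrase. Its singular verb also allows nature and severity to be read as one profile that fails if either part fails.

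Much of this stands. A reader might infer from 11.1.5 that such a reaction is, for this protocol, unexpected and yet not a SUSAR. The document does not support that flat conclusion, because the sections that trigger reporting capture it. What the reply does not remove is the second definition. Section 11.6 uses the word unexpected without pointing to 11.1.3, and a reader looking up SUSAR lands on 11.1.5. The loose reading of *and* is possible, but 11.1.3 uses *or* for the same test two definitions earlier, so the text does not require it.

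Two further inferences should be resisted.

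- **That unlisted severity or outcome is a likely route to unexpectedness for this drug.** That depends on what section 4.8 of the product summary lists, which the protocol does not reproduce.
- **That the reporting clock is delayed by up to 24 hours.** The limits run from a point "after the trial team and Sponsor has first knowledge of the minimum criteria for expedited reporting", and 11.5 gives the CI 24 hours to inform the Sponsor. But the phrase can be read as the earliest knowledge of either party. The Sponsor is also itself among those to be notified under 11.6.1, so a clock that waits for the Sponsor's knowledge would be circular. The wording is ambiguous; it does not establish a delay, and it is a separate matter from what a SUSAR is.

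**Conclusion.** The protocol contains two SUSAR definitions that do not agree. Section 11.1.5, read literally, is strictly narrower than 11.1.3 with 11.6 and 11.6.3.1(c), and it omits the outcome criterion altogether. For a serious suspected reaction of listed nature but unlisted severity or outcome, the two routes give opposite answers.

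The practical risk is limited. It arises only if an assessor applies 11.1.5 alone and takes *and* at its word. Even then the event is still reported as an SAE to the CI and the Sponsor under 11.5; what could be lost is the expedited report and the associated unblinding. The number of cases cannot be derived from the document. The endpoint, analysis, sample size and arms are unaffected. This is an internal inconsistency in an operative safety definition. It is worth correcting because the definition governs expedited reporting and errs in one direction only.

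**What to change.** Reconcile 11.1.5 with 11.1.3 and 11.6. The simplest way is to have 11.1.5 define a SUSAR as a suspected serious adverse reaction that is unexpected as defined in 11.1.3, that is, with nature, severity or outcome not consistent with the RSI. A cross-reference from 11.6 to 11.1.3 would leave a single test throughout.

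As an optional clarification in the same amendment, 11.6.2.1 and 11.6.2.2 could state whose first knowledge starts the 7- and 15-day limits.

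The cost is a few words in the next protocol amendment. Assessors who had been working from 11.1.5 might submit a few more expedited reports.
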